### **Hypotheses**

The purpose of this study is to: 1. Complete an effectiveness trial of Living Well in the VA context, and; 2. Concurrently collect, in the context of a process evaluation, important contextual and cost information that can help speed throughout to public health impact.

For the remainder of this protocol all required descriptions will be presented first for the EFFECTIVENESS TRIAL and second for the PROCESS EVALUATION.

Objectives and hypotheses for the EFFECTIVENESS TRIAL:

Objective: Complete a randomized controlled effectiveness trial comparing Living Well to a general medical illness education and support group among SMI Veterans with co-occurring chronic medical conditions. Those receiving Living Well will demonstrate:

Hypotheses for EFFECTIVENESS TRIAL:

Primary Hypotheses (regarding functional and service-related outcomes)

Hypothesis 1: Improved general, physical, and emotional functioning post intervention.

Hypothesis 2: Lower rates of medical emergency room use for management of a chronic medical condition six months post randomization.

Secondary Hypotheses (regarding more proximal attitudinal and behavioral outcomes)

Hypothesis 3: Improved health-related self-efficacy and patient activation post intervention. Further, such improvements will mediate the effects of the functional and service outcomes specified above.

Hypothesis 4: Improved self-management behaviors post intervention. Further, such improvements will mediate the effects of the functional and service outcomes specified above.

Secondary Hypothesis (regarding retention of intervention effects)

Hypothesis 5: Sustained improvements across functional, attitudinal and behavioral outcomes for three months after completing treatment.

Objective for the PROCESS EVALUATION:

Complete a well specified process evaluation based on the RE-AIM evaluation framework to better understand contextual factors that can improve future adoption, implementation and sustainability of the Living Well intervention in the VA system of care. A cost analysis will also be completed as part of this effort.

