## **Procedures Defining the Delivery of the Experimental and Control Condition Interventions:**

### **Living Well (Experimental Condition):**

Living Well will be implemented as a 12 session small-group intervention (4-8 persons). Groups will meet weekly for 75 minutes for three months (12 sessions). The 12 session weekly curriculum will be delivered as a series of 4 three-session modules. Module one provides an overview of the full course and begins with a review of the key concepts of self-management and proceeds with sessions focused on learning the behavioral action planning and problem solving skills that are used across the remaining modules. Since the first module of this intervention contains the fundamental building blocks that will be utilized throughout the intervention, participants who miss any of the first 3 start-up sessions will be offered an opportunity to meet individually with a facilitator to review the missed session content. These review sessions can be completed by the participant either in person or by phone. Remaining modules focus on a variety of wellness topics including health eating, medication management, and communicating with providers. After completing the 12 weekly groups, participants will return to complete once monthly booster group sessions for the next three months. All Living Well group sessions and booster sessions will be video recorded. The Living Well intervention will be led by a trained interventionist and co-facilitated by a peer provider using the manualized curriculum developed in our previous research. The pairing of a trained peer and professional affords maximal flexibility and will help support uptake of the intervention. This study is based on the intent-to-treat model. Regardless of level of participation in the Living Well groups, all randomized participants will be eligible and contacted to schedule post treatment follow-ups for this study.

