### **Medical Illness Education and Support Group (Comparison Condition):**

We selected a comparison condition that would provide parallel focus (i.e. medical illness) but not include use of the core ingredients undergirding the Living Well intervention including behavioral action planning, problem solving, in-session and between session practice using specific disease self-management techniques and involvement of peer co-facilitators to enhance modeling and improve self-efficacy and activation. As with Living Well, the content of the intervention will have broad applicability across diverse chronic disease conditions. The comparison condition will be a once-weekly support and education group focusing on living with a chronic medical condition. All Medical Illness Education and Support group sessions will be video recorded. Groups will be led by a single professional interventionist and will include standardized didactic review of common challenges experienced by those living with a wide range of chronic medical illnesses and related behavioral and lifestyle self-management techniques. Each session will follow a basic structure that includes a review of the material presented in the previous session, new education content and discussion. This study is based on the intent-to-treat model. Regardless of level of participation in the Medical Illness Education and Support group, all randomized participants will be eligible and contacted to schedule post treatment follow-ups for this study.

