Hypothesis 4 (H4): Compared to those receiving a general medical illness education and support group, participants receiving Living Well will report improved self-management behaviors. Further, such improvements will mediate the effects of the functional and service outcomes specified above.

We will use a parallel model as for Hypothesis 1 to compare the two conditions on the self-management behavior scales at post-treatment. The tests of mediation will be directly parallel to those described for the test of mediation in Hypothesis 3 for the functional and ER use outcome variables.

Secondary Hypothesis 5: Living Well participants will sustain improvements across functional, attitudinal and behavioral outcomes at follow-up (3 months post-treatment).

We will test sustained improvement by testing the null hypothesis of no difference in change from randomization to the 3-month follow-up assessment (2-sided test) which will be the test that the coefficient for the study condition-by-time interaction term in the primary model (see H1) is zero. This hypothesis applies only to outcomes obtained from interview, not for ER visit and other 6-month service utilization variables. All available data will be included in these intent-to-treat analyses. The aforementioned analysis plan regarding dropout will be used.

Exploratory analyses: We will conduct several exploratory analyses.

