One, in the Living Well group we will utilize data collected at consent to examine outcome trajectories and change in trajectories in the transition from the pre-intervention period (2 months on average) to the intervention period (randomization to post-tx; 3 months) and the post-intervention period (post-tx to follow-up; 3 months). For this analysis, time will be treated as continuous as time from consent to randomization will vary. A spline will be used starting at randomization to detect change in slope when the intervention commences. This analysis will allow comparison of the Living Well group to themselves prior to intervention. Two, we will examine whether improvements on primary and secondary outcomes in the Living Well condition relative to the control condition differ among 5 chronic medical condition subgroups: a) diabetes; b) a respiratory illnesses (including asthma and COPD); c) arthritis, d) a cardiovascular condition (e.g. congestive heart failure); or e) two or more of (a) thru (d). We will describe treatment effects by chronic illness sub-group, computing average treatment effect for each subgroup. We will also add the 3-way interaction term between study condition, time, and chronic illness category to the primary analysis models in order to perform a global test of differential improvement on outcomes by

chronic medical condition subgroup.

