#### **EFFECTIVENESS TRIAL:**

Veterans will be paid \$40 for completion of each of the four study interviews for a total of \$160. The first interview will be completed at consent. The second interview (randomization) will be right before the groups start. The third interview will be right after the group sessions are completed (post-treatment) and the fourth interview will be about 3 months after the participant completes group (3 months post-treatment assessment).

Some participants may be asked to come in for an additional interview with study staff after completing their group meetings. If they agree to come in for this interview, they will be paid an additional \$40.

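### Hypothesis 5 claims retention for three months after treatment, but Living Well runs monthly booster groups through those same months

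*Protocol*

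**What the plan says.** The Hypotheses section places Hypothesis 5 under the heading "Secondary Hypothesis (regarding retention of intervention effects" and words it as "Sustained improvements across functional, attitudinal and behavioral outcomes for three months after completing treatment". The Data Analysis section repeats it as "Living Well participants will sustain improvements across functional, attitudinal and behavioral outcomes at follow-up (3 months post-treatment" and tests it as the between-arm difference in change from randomization to the month-6 assessment, using the condition-by-time coefficient of the Hypothesis 1 model. The exploratory trajectory analysis in the same section calls months 3 to 6 "the post-intervention period (post-tx to follow-up; 3 months". The Cost/Payment section says that the "fourth interview will be about 3 months after the participant completes group (3 months post-treatment assessment".

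The intervention is set out under Living Well (Experimental Condition). The weekly phase is described as "Groups will meet weekly for 75 minutes for three months (12 sessions". After it, "participants will return to complete once monthly booster group sessions for the next three months".

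For the control arm, the corresponding section says: "The comparison condition will be a once-weekly support and education group focusing on living with a chronic medical condition". It mentions no boosters and does not rule them out.

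**The concern.** The hypothesis and the intervention schedule do not fit together. A retention claim needs an interval in which the intervention has stopped, so that what remains can be measured. The Living Well arm has no such interval of three months, because group contact continues monthly up to or close to the final interview. Neither the text of Hypothesis 5 nor its analysis mentions this.

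What is at stake is what a positive result would be taken to mean. As worded, it would be read as improvement that lasted after the programme ended. The trial also aims to produce an implementation toolkit and an estimate of operating costs. A reader who believed that the 12 sessions alone carry the benefit to month 6 might deliver the programme without boosters, which is a version this trial does not test.

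**Working it through.** The protocol gives no power or sample-size figure for Hypothesis 5, so there is no stated number to reproduce. The check compares the schedule with the claim.

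**1. Timeline.** The Cost/Payment section puts the randomization interview just before the groups start. Counting from randomization:

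| Months | Living Well | What the protocol calls the period |
|---|---|---|
| 0 to 3 | 12 weekly sessions | intervention |
| 3 to 6 | monthly boosters for three months | post-intervention; follow-up after treatment |
| 6 | final interview | three months after treatment |

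The booster months and the retention months are the same months.

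**2. Share of scheduled contact.** One booster a month for three months is 3 sessions. Their share of all scheduled group sessions is 3 / (12 + 3) = 3/15 = 20%, and all of them lie inside the Hypothesis 5 interval.

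**3. Booster-free gap before the month-6 interview.** Exact booster dates are not given. Assume boosters one month apart, with the first after month 3 and no later than month 4. Then last booster = first + 2 and gap = 6 − last.

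| First booster (month) | Last booster (month) | Gap (months) |
|---|---|---|
| 3.25 | 5.25 | 0.75 |
| 3.5 | 5.5 | 0.5 |
| 4.0 | 6.0 | 0 |

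The gap is zero to just under one month, whereas the hypothesis implies three.

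**4. Does any planned analysis separate the two explanations?** The Hypothesis 5 test is the condition-by-time coefficient with time entered as continuous (0, 3, 6). That is one slope difference over the whole six months and does not isolate what happens after month 3. The exploratory spline analysis uses the Living Well arm only, where everyone is scheduled for boosters. Neither can distinguish persistence of the course from the effect of continued contact.

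**5. Does the control arm's status matter?** If control has no boosters, the arms also differ in ongoing contact during months 3 to 6. If control does have them, those months are still not free of intervention in either arm. The retention reading fails in both cases.

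**The case against.** The best reply is that the protocol uses the word treatment for the weekly course. Living Well is introduced as a 12-session programme, the post-treatment assessment is fixed at three months, and boosters are named separately from the group sessions. On that usage the hypothesis refers to the three months after the weekly course, boosters are maintenance within follow-up, and no sentence promises a contact-free interval. The boosters are also openly described, and in an effectiveness trial the package as delivered is a legitimate target.

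Much of this stands. The schedule is disclosed, the randomized month-6 comparison is sound, and the labels can be read as shorthand for assessment times. It is also true that the 20% share counts contacts and says nothing about how much of any month-6 effect the boosters could produce; their length and content are not stated. The silence about control boosters proves nothing either way.

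The reply does not rescue the retention claim. Even if boosters are called maintenance, an effect measured while maintenance contact continues is not evidence of what remains after the course has ended. The boosters are listed as part of the experimental condition, and nothing in the protocol qualifies Hypothesis 5 to take account of them.

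**Conclusion.** The concern holds. The month-6 contrast estimates the effect of 12 sessions plus monthly boosters against the comparison group. It does not estimate retention after Living Well has stopped, and a positive result should not be reported as such.

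The limit is on attribution only. It affects one secondary hypothesis and the label of one exploratory analysis. The contrast remains a valid randomized comparison, a null result remains interpretable, and Hypotheses 1 and 2 make no retention claim. The overlap of boosters with months 3 to 6 follows directly from the protocol; only the size of the final gap (zero to under one month) depends on the assumed booster dates. This should be corrected, but it does not threaten the primary analyses.

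**What to change.** Keep the contrast and model as planned, and change the wording:

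- **Hypotheses and Data Analysis:** restate Hypothesis 5 as the between-arm difference in change from randomization to six months for Living Well including its monthly boosters. Remove the retention heading and the reference to treatment having been completed.
- **Exploratory trajectory analysis:** call months 3 to 6 the booster period.
- **Minor tidying:** in Cost/Payment, date the fourth interview as about six months after randomization, as the design section already does. In the comparison-condition section, state whether control receives boosters.

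The cost is wording only, with no change to visits, sample size, alpha or model. The trial gives up a claim that the 12-session course alone has durable effects, which this design cannot support.

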### **Medical Illness Education and Support Group (Comparison Condition):**

We selected a comparison condition that would provide parallel focus (i.e. medical illness) but not include use of the core ingredients undergirding the Living Well intervention including behavioral action planning, problem solving, in-session and between session practice using specific disease self-management techniques and involvement of peer co-facilitators to enhance modeling and improve self-efficacy and activation. As with Living Well, the content of the intervention will have broad applicability across diverse chronic disease conditions. The comparison condition will be a once-weekly support and education group focusing on living with a chronic medical condition. All Medical Illness Education and Support group sessions will be video recorded. Groups will be led by a single professional interventionist and will include standardized didactic review of common challenges experienced by those living with a wide range of chronic medical illnesses and related behavioral and lifestyle self-management techniques. Each session will follow a basic structure that includes a review of the material presented in the previous session, new education content and discussion. This study is based on the intent-to-treat model. Regardless of level of participation in the Medical Illness Education and Support group, all randomized participants will be eligible and contacted to schedule post treatment follow-ups for this study.

## **2. Procedures Associated with the PROCESS EVALUATION**

We propose to complete a process evaluation based on the RE-AIM evaluation framework to better understand contextual factors that support the conduct of the proposed trial and that will affect future efforts to implement and sustain the Living Well intervention in the VA system of care. The proposed evaluation also provides a distinct and complementary avenue for understanding differential outcomes across conditions. This evaluation will integrate findings from two streams of inquiry: 1) A qualitative study that includes combines focus groups and/or individual interviews conducted both before and after the clinical trial, and; 2) a cost analysis focused on implementation/operating costs and cost consequences. The PROCESS EVALUATION will be conducted both BEFORE the EFFECTIVENESS Version 9, 5/1/2015

## Trial and AFTER the EFFECTIVENESS TRIAL.

### Pre-trial focus and methods:

Prior to initiating the effectiveness trial, we will conduct a series of qualitative focus groups and/or individual interviews with a range of key stakeholders to: 1) Identify obstacles and barriers that might impede the proposed trial, and; 2) collect contextual information that will inform future dissemination and sustainability of the Living Well intervention in the broader VA context. The discussion guide used to help facilitate these groups or interviews is attached to this protocol submission.

Methods: We will complete focus groups and/or individual interviews with local clinicians and administrators working in implementation sites. Queries will focus on clinician/administrator perceptions of how well they think Living Well fits with existing clinic services for Veterans with co-occurring medical conditions, and their perceptions of potential barriers and facilitators associated with adopting the Living Well intervention for use in their programs/clinics. The groups or interviews will also discuss how to best secure buy-in from program administrators, clinicians and service recipients to support Living Well during the trial and anticipated challenges to securing the resources needed to support and sustain Living Well beyond the trial. A facilitator guide to help focus group discussion is attached to this protocol.

All group meetings or interviews will be digitally recorded and transcribed by a staff member listed on this protocol. Copies of transcripts, along with field notes and observations made by focus group leaders, will be used to draft summaries for each group session. All participants will be invited to review these documents and their feedback will be used to refine our summaries.

### Post-trial focus and methods:

After completing the EFFECTIVENESS trial, we will conduct focus groups and in-depth individual interviews with Veteran study participants, Veterans who served as peer co-facilitators in the Living Well condition, and various stakeholders involved in the pre-trial evaluation to: 1) extend and enhance our understanding of intervention outcome and processes, and; 2) inform the development of an implementation toolkit to support future dissemination efforts. The discussion guides for all of these are attached to this CICERO submission.

We will conduct a post-trial focus group with the same people who participated in the pre-trial groups. Specifically, this will involve re-convening the local clinicians and administrators. Preliminary results from the trial will be shared and discussed in relation to implications for local programming. Other questions will focus on their perceptions of how study participation impacted Veterans receiving services in their program, and what resources/assistance the programs feel would be needed to support continued implementation of the Living Well intervention. As such the post-trial focus groups will give us a distinct and complementary avenue (in combination with results from the trial) to understanding outcomes associated with receipt of the intervention and processes of implementation. All post-trial focus groups will be audio recorded, transcribed, reviewed by study team, and summaries distributed to participants for feedback before they are used to write summary documents.

Across both conditions, we will also complete in-depth individual interviews with a sub-set of Veterans who participated in the trial, purposefully selected to include some who completed the intervention (target n=10) and some who decided to discontinue (target n=10). These interviews will focus on why Veterans decided to enroll, their initial expectations, and what led to their decision to continue or discontinue.

Among those who completed Living Well, we will explore the impact of the intervention on their self-

management challenges during the intervention and how they have made use of knowledge and skills learned from Living Well since completing the intervention. We will also complete in-depth individual interviews with individuals who served as peer co-facilitators for the Living Well intervention. These interviews will focus on understanding how leading the Living Well groups influenced their own self-management, and what they observed among the participants. Interviews will also focus on their experiences of the training and support they received in preparation and while delivering the Living Well intervention.

All the interviews will be semi-structured with open-ended questions, will last approximately 1 hour and will be conducted in private by study team members. They will be digitally recorded and transcribed. In addition, the interviewer will take notes during the interview and record her observations immediately after the session.

Analytic methods for both focus groups and interviews include coding the interview data (assisted by Atlas.ti software) into categories and using those categories to build higher order concepts and themes. Themes and categories will be sorted and synthesized and examined for interrelationships, checking back to the data frequently. These connections will potentially lead to the development of a conceptual or theoretical framework depicting how various elements of Living Well are experienced, the impact the intervention has on important Veteran level outcomes, and the role Veterans might play in future dissemination efforts.

The PROCESS EVALUATION will also include a COST ANALYSIS.

We will assess the average cost of a Living Well program, including implementation and operating costs, and complete an initial analysis of VA health care cost consequences of Living Well to assess whether participation in Living Well results in any savings (i.e., “cost offsets”) to the VA healthcare system. The analysis will apply the opportunity cost approach from the perspective of the VA health care system (i.e., the “payer perspective”). The approach will be consistent with methods recommended for economic evaluation studies. All analyses will use VA administrative and chart data collected as part of this study. Data from the Services Utilization Record Form (SURF) described and cited above, will also be used to inform cost analyses.

The PROCESS EVALUATION will also include consulting with an Advisory Board.

We will hold periodic calls with a board of advisors to discuss how to use what we learn in the study to inform future implementation considerations. Advisors will include key stakeholders at the local, VISN and National VA level. No individual level data or PHI will be shared with this board. Instead, the board will only discuss anticipated challenges and opportunities to support ultimate uptake within the VA system of care and the intervention being evaluated in the context of this study.

